NCT 03121794

Ultrasonographic Identification of the Proximal Humerus Landmarks for Intra-Osseous Vascular Access across Different Body Habitus

An observational study to determine if there is consistency in ultrasonographic landmark identification of the proximal humerus across various body habitus

Original Date: July 11, 2016 (version 1.0)
Final version Date: **12/01/2016**

Names and Addresses of:

Principal Investigator	Name:	[name]
	Address:	Cleveland Clinic Department of Cardiothoracic Anesthesiology [name]
	[contact]
	Email:	[contact]
Co-investigator	Name:	[name]
	Address:	Cleveland Clinic Department of General Anesthesiology [name]
	[contact]
	Email:	[contact]
Co-investigator	Name:	[name]

	Address:	Cleveland Clinic Department of Cardiothoracic Anesthesiology [name]
	[contact]
	Email:	[contact]

Study Summary

Title	Ultrasonographic identification of the proximal humerus landmarks for Intraosseous Vascular access across different body habitus
Short Title	Ultrasonographic landmark identification of the proximal humerus
Principal Investigator	[name]
Primary Objectives	Evaluate whether discrete landmarks of the proximal humerus can be identified using ultrasound in patients with various body habitus and BMI.
Primary Endpoints	Ability to identify the following 6 anatomical landmarks for proximal humerus interosseous venous access with ultrasound: 1. Humeral shaft, 2. Surgical neck of the humerus, 3. Lesser tubercle, 4. Greater tubercle, 5. Intertubercular sulcus 6. Target site for needle insertion in the greater tubercle.
Secondary Objectives	
 - Evaluate the time used to identify all 6 anatomical landmarks using ultrasound. - Evaluate the depth of each landmark from skin under ultrasound. - Correlate the Arm thickness with the depth of the anatomical structures. - Correlate the BMI with the depth of the anatomical structures.
Secondary Objectives Measures	
 - Time used to identify all 6 anatomical landmarks in seconds. - Depth of each anatomical landmark from skin in centimeters.
Study Design	A single institution observational study
Inclusion Criteria	
 1- Males or females 18 years of age or older. 2- $BMI \geq 18.5$
Exclusion Criteria	
 1. Limited mobility/ range of motion of arms 2. Prior surgical intervention on shoulder or humerus 3. History of arm dislocation with internal rotation 4. History of arm fracture 5. BMI in ranges: 25.1 – 29.9, 35.1 – 39.9
Expected Sample Size	30 Patients (60 exams)
Statistical Methodology	We will summarize the total number of correctly identified landmarks per patient overall and by BMI category. We will also estimate the incidence of correctly identifying all landmarks per patient with a 95% bootstrap confidence interval.

List of Abbreviations

Abbreviation	Definition
BMI	Body Mass Index
CFD	Color Flow Doppler
CV	Central Venous
IO	Intraosseous
PH	Proximal Humerus
PHIO	Proximal Humerus Intraosseous
PHIOVA	Proximal Humerus Intraosseous Vascular Access
PIV	Peripheral Intravenous

1 Introduction

This document is a protocol for a human research study. This study is to be conducted according to US and international standards of Good Clinical Practice (FDA Title 21 and International Conference on Harmonization guidelines), applicable government regulations and Cleveland Clinic research policies and procedures.

1.1 Background and Rationale

Establishing vascular access is of vital importance during resuscitation of cardiac arrest, trauma and during various intraoperative scenarios. During cardiac arrest minimizing time wasted without performing chest compression is vital to successful resuscitation, therefore, being able to establish vascular access quickly can save lives[1]. Intraoperatively, the ability to rapidly obtain vascular access is crucial to maintain hemodynamic stability. Similarly, having adequate vascular access is the cornerstone for resuscitation in trauma patients.

Three main forms of vascular access are used in the scenarios above: peripheral intravenous (PIV), Central venous (CV) and intraosseous (IO). Of the different types of vascular access PIV and CV access have drawbacks when used during resuscitation[2], because they can be difficult to obtain when patients are volume depleted as in cases of trauma. Attempting CV access has numerous risks with complications occurring in up to 33% of attempts. These include failed placement (22%), arterial puncture (5%), catheter malposition (4%), pneumothorax (1%) and asystolic cardiac arrest (<1%)[3]. Attempting to obtain CV access may also disrupt chest compressions in cases of cardiac arrest. Intraosseous access has been used in scenarios where PIV and CV access is difficult or impossible to obtain. Pharmacokinetic studies and standard practice support the bioequivalence of intraosseous and intravenous administration of common

medications[4]. Intravascular depletion does not hinder attempts at IO access, and as the insertion sites are peripheral to the heart, insertion can be done avoiding interruptions in chest compressions. Obtaining proximal humerus interosseous (PHIO) access may also be faster than obtaining both PIV and CV access with a relatively low complication rate[2]. In one survey of Scandinavian users, complications of IO included difficulty in identifying correct anatomical site (3%), extravasation (3.7%), displacement after insertion (8.5%), and very rarely late complications including compartment syndrome (0.6%), osteomyelitis (0.4%) and skin infection (0.3%)[5].

The site that has been used most commonly for IO access has been the proximal anterior tibia because of ease of landmark identification and provider familiarity. The proximal humerus (PH) has recently gained more attention and is a viable alternative to the anterior tibia because of decreased pain with initial bolus, decreased medullary pressure resulting in more rapid fluid delivery and is in closer proximity to the heart[6].

Proximal humerus interosseous access relies on landmark identification of the greater tubercle via palpation of the surgical neck of the humerus. This method can be especially difficult in patients with prominent deltoid musculature or adipose tissue overlying these landmarks. Failure to identify landmarks is an absolute contraindication to IO access[1]. Success rates for PHIO needle insertion have been cited as low as 76% in one study compared to 92% for proximal tibial insertion[7]. Moreover, a failed IO needle insertion precludes the immediate use of the same site for another trial.

Ultrasound identification of PH structures on cadavers has recently been described in the literature and has the promise of increasing the success rate of what is now considered a blind procedure[8]

1.2 Clinical Data to Date

Ultrasound identification of proximal humeral structures is a novel concept with no current case reports or clinical trials demonstrating its use in clinical practice.

A correspondence letter by Bustamante et al.[8] demonstrated the use of ultrasound to identify PH structures on a cadaver model. Structures identified were the greater and lesser tubercles, intertubercular groove and surgical neck. Identification of these structures are necessary for PHIO needle placement. A 13-6 MHz ultrasound linear probe (SonoSite Inc; Bothell, Washington, USA) was used to identify these structures on 5 cadavers with body max indexes (BMI) ranging from 20 – 35. All structures were relatively superficial, within 3cm from the skin. Once landmarks and target site were identified, an IO needle was inserted and placement was confirmed with color flow doppler (CFD).

Failure to identify proximal humeral structures is considered an absolute contraindication to attempting PHIO placement. Prominent deltoid musculature and adipose tissue overlying proximal humeral landmarks can make identifying proximal humeral structures by palpation difficult if not impossible. As failed PHIO access of one arm precludes the use of the same arm for subsequent trials the first attempt must be optimized to allow for the greatest chance for success. If ultrasound is found to successfully identify all landmarks, even in patients with higher BMI's, failure to identify landmarks by palpation will no longer be considered an absolute contraindication.

2 Objectives

2.1 Primary Objectives:

Estimate the ability to successfully identify each of the six proximal humerus anatomical landmarks required for proximal humerus interosseous vascular access (PHIOVA), using ultrasound in patients with different body habitus: BMI 18.5-25 kg/m², BMI 30-35 kg/m², and BMI > 40 kg/m².

2.2 Secondary Objectives:

- Estimate the time used (in seconds) to identify all 6 anatomical landmarks using ultrasound in patients with different body habitus.
- Estimate the depth of each landmark (in centimeters) from the skin using ultrasound in patients with different body habitus.
- Estimate the correlation between upper arm thickness and the depth of the anatomical structures.
- Estimate the correlation between BMI and the depth of the anatomical structures.

3 Primary hypothesis

We will test the hypothesis that all 6 anatomical landmarks for proximal humerus interosseous venous access can be identified using ultrasound in all patients irrespective of their BMI, or mid upper arm circumference.

4 Study Design

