6.1 Primary Analysis

We will summarize the success of landmark identification overall and by BMI category. Landmark identification is considered successful if all 6 landmarks are identified correctly. We will estimate the incidence of correct identification of all landmarks with a 95% bootstrap confidence interval. We will use bootstrap confidence intervals instead of binomial confidence intervals to account for intra-subject correlation because landmark identification will be performed twice per subject.

We will also report the median [Q1, Q3] of the mean number of landmarks identified correctly per patient overall and by BMI category. Results will be presented in tables and appropriate graphs. Descriptively, we will summarize the percent of correct identification by landmark location.

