6.2 Sample Size Considerations

We will enroll 30 patients, with 10 patients in each BMI category: BMI 18.5-25 kg/m², BMI 30-35 kg/m², and BMI > 40 kg/m². Given that investigators will be highly trained, we conservatively assume all landmarks will be identified 80% of the time. We expect very weak intra-subject correlation. Ignoring intra-subject correlation, we expect 95% confidence interval widths as small as 0.22 for overall incidence of correct identification and 0.38 within each BMI category. Confidence intervals will be somewhat larger depending on the strength of intra-subject correlation. Confidence interval widths will be narrower if investigators are more than 80% successful at identifying landmarks.

Study enrollment will start with 3 pilot patients with different BMI, but they will not be included in the statistical analysis. Thereby, a total of 33 patients will be enrolled in our study

References

1. Anson, J.A., *Vascular Access in Resuscitation. Is There a Role for the Intraosseous Route?* Anesthesiology, April 2014. **120**(4): p. 1015-31.
2. Paxton JH, K.T., Klausner HA *Proximal Humerus Intraosseous Infusion: A Preferred Emergency Venous Access.* The Journal of Trauma, September 2009. **67**(3): p. 606-11.
3. Eisen LA, N.M., Berger JS et al., *Mechanical complications of central venous catheters.* Journal of Intensive Care Mericine, 2006. **21**(40).
4. VonHoff DD., K.J., Burris HA. III, Miller LJ., *Does intraosseous equal intravenous? A pharmacokinetic study.* American Journal of Emergency Medicine, 2008. **26**: p. 31-8.
7. Kovar J, G.L., *Alternate route: the humerus bone – a viable option for IO access.* Journal of Emergency Medical Services, August 2010. **35**(8): p. 52-9.
8. Bustamante S, C.S., *Ultrasound to Improve Target Site Identification for Proximal Humerus Intraosseous Vascular Access.* In press Anesth Analg, 2016.

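### Section 3 promises to test that all six landmarks can be found in all patients: one miss refutes this, no sample can confirm it, and the plan contains no test of it

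*Combined protocol and SAP*

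**What the plan says.** Section 3 (Primary hypothesis) is one sentence: "We will test the hypothesis that all 6 anatomical landmarks for proximal humerus interosseous venous access can be identified using ultrasound in all patients", and it continues "irrespective of their BMI, or mid upper arm circumference".

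The rest of the plan is about estimation:

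- Section 2.1 sets the primary objective as estimating how well each of the six landmarks can be identified in three BMI groups.
- Section 6.1 counts an exam as a success only if all six landmarks are correctly identified, and then says: "We will estimate the incidence of correct identification of all landmarks with a 95% bootstrap confidence interval". It adds summaries by BMI category and by landmark. It gives no null value, significance level, performance threshold or decision rule.
- Section 6.2 (Sample Size Considerations) sizes the study on interval width. On numbers: "We will enroll 30 patients, with 10 patients in each BMI category". On the success rate: "we conservatively assume all landmarks will be identified 80% of the time".
- The study summary gives 60 exams from 30 patients, so each patient contributes two and each BMI band 20.

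**The concern.** The only primary hypothesis in the protocol is universal, and the analysis section has nothing that could decide it in its favour. A reader cannot tell from the protocol which result would support it.

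The risk is mainly on one side. If all exams succeed, section 3 taken literally invites the conclusion that ultrasound works in all patients. Section 1.2 attaches weight to that: it says that if ultrasound finds all landmarks, even at higher BMI, failed palpation will cease to count as an absolute contraindication. The evidence for the higher-BMI groups would be 10 patients in each of two bands. The exclusion criteria also remove BMI 25.1–29.9 and 35.1–39.9, and inclusion starts at 18.5, so a claim that holds whatever the BMI reaches beyond the people sampled.

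**Working it through.** **Inputs.** 30 patients, 10 per BMI band (section 6.2, Sample Size Considerations); 60 exams, so 20 per band (study summary); planning success rate 0.80 per exam (same section 6.2); success means all six landmarks (section 6.1).

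**1. The plan's own figures.** The stated 95% interval widths are 0.22 overall and 0.38 per band, ignoring correlation between a patient's arms. Exact (Clopper-Pearson) intervals reproduce both:

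- 48/60: 0.677 to 0.892, width 0.2155, rounds to 0.22.
- 16/20: 0.563 to 0.943, width 0.379, rounds to 0.38.

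The sizing arithmetic is sound and is not part of this point.

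**2. Chance of no failure.** For true per-exam rate p, this is p^60 if exams are independent and p^30 if a patient's two arms always agree. Both require success in both arms of every patient.

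| True rate p | p^60 | p^30 |
|---|---|---|
| 0.80 | 0.0000015 | 0.0012 |
| 0.95 | 0.046 | 0.215 |
| 0.98 | 0.298 | 0.545 |
| 0.99 | 0.547 | 0.740 |

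At the planning value a miss is almost certain. At 0.98, where the universal claim is still false, the study would nevertheless show no failure with probability 0.30 to 0.55. In one BMI band, 20/20 has probability 0.95^20 = 0.36 at a true rate of 0.95. A clean run is therefore weak evidence for 100%.

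**3. What a clean run can support.** With n successes out of n, the exact two-sided 95% lower limit is 0.025^(1/n).

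| Unit | Overall | Per BMI band |
|---|---|---|
| Exams, treated as independent | 60/60: 0.940 | 20/20: 0.832 |
| Patients with both arms successful | 30/30: 0.884 | 10/10: 0.692 |

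The second row answers a different question, since a patient counts only if both arms succeed. It also serves as the cautious limit for the exam proportion: if the arms are fully correlated, 60 exams carry the information of 30. The plan expects very weak correlation, in which case the exam-level limits lie near the first row.

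**4. No sample reaches 1.00.** The number of failure-free independent units needed for a lower limit above p0 is the smallest integer n ≥ ln(0.025)/ln(p0): 36 for 0.90, 72 for 0.95, 368 for 0.99. These thresholds are illustrative, as the plan sets none. For p0 = 1.00 no finite n suffices.

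**5. What the planned interval would show.** If every exam succeeds, every bootstrap resample of patients also has proportion 1.00, so the interval is 1.00 to 1.00. It would look like proof of the hypothesis.

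**The case against.** The strongest defence is that section 3 is one sentence out of line with a plan that is otherwise consistently about estimation. The objective, the primary analysis and the sizing all concern a proportion and its interval, and those results will be reported whatever section 3 says. This stands, and it limits the repair to wording plus one interval rule. It does not remove the point, because this sentence is the sole primary hypothesis, has its own heading and says that it will be tested.

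A reader might go further and infer three things that the documents do not support:

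- *That the plan's own 80% makes the hypothesis false.* The plan calls 80% conservative and allows for better: "Confidence interval widths will be narrower if investigators are more than 80% successful at identifying landmarks". It is a cautious sizing value, and the conflict arises only if it is also the true rate. The near-certain miss at 80% also assumes that both arms must succeed. Section 4.2 scores each arm, so that reading is reasonable, but section 3 speaks of patients. If either arm sufficed, independent exams at 80% would give (1 − 0.2²)^30 = 0.96^30 = 0.29.
- *That the hypothesis cannot be answered at all.* It can be answered in one direction: a verified miss refutes it, and that inference is valid.
- *That the study can only end in a misleading conclusion.* Section 6.1 provides incidence with an interval, results by BMI category and results by landmark. These are informative with or without a miss.

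**Conclusion.** The point holds as a mismatch between section 3 and the rest of the plan. The universal hypothesis can be refuted but never confirmed, it has no planned test or success criterion, and it goes beyond an estimation objective that the study can meet. The planned estimates remain valid. The unsound step would be to conclude that the method works in all patients from a run of successes in this sample.

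As to size, even a perfect result leaves room for a failure rate of up to 6% of exams overall and 17% in a band if exams are independent. For patients with at least one unsuccessful arm, the figures are 12% overall and 31% in a band. These are one minus the limits in the second table, at two-sided 95% confidence. That the hypothesis cannot be confirmed depends neither on the 80% value nor on how the two arms are combined.

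**What to change.** 1. Replace the section 3 sentence with, for example: *We will estimate, overall and within each of the three BMI bands studied, the proportion of exams in which all six landmarks are identified. Conclusions will rest on the lower 95% confidence limit, not on the absence of failures.* This removes the promise to test and the reference to all patients. The arm-circumference clause goes too, which loses no planned analysis, because section 6.1 breaks identification down only by BMI category.
2. Keep the per-landmark summaries in section 6.1; they serve objective 2.1.
3. Add to section 6.1 that, if a group has no failures, its lower limit will come from an exact (Clopper-Pearson) interval because the bootstrap collapses to 1.00. Name the unit in advance. The patient-level count is the cautious choice, since the exam proportion cannot be lower than the proportion of patients with both arms successful.
4. Add the best achievable lower limits to the sample size section with units matched: 94% overall and 83% per band for exams treated as independent; 88% and 69% for patients with both arms successful.
5. If a pass mark is wanted, state it before enrolment as a value for the lower limit.

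No patients, procedures or data are added. The cost is a protocol wording change, one fallback interval and a more modest headline claim.

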4.1 General Design

- An observational study performed on adult patients undergoing general, cardiac, thoracic or vascular surgery.
- Demographic data collected include age, sex, weight (kg), Height (cm)
- BMI, and mid upper arm circumference will be measured or calculated for all subjects.

The study procedure will be performed on each patient by two out of three investigators trained on performing an ultrasonographic exam of the proximal humerus using a linear probe. All investigators have at least one year of experience in ultrasonography with the linear probe and have participated in at least three (3) PHIO access workshops. ([name], [name], and [name]). Two investigators will perform an ultrasonographic exam on each patient, with one investigator examining each side. Investigator A will perform the exam and identify all 6 landmarks with ultrasound, while investigator B will time the exam starting from when the ultrasound probe is handled till all landmarks are identified. Investigator B's role is also to verify that landmarks are identified and document how many of the landmarks were seen from zero to six out of six per arm. After the exam is complete, the roles of investigator A and B are then

switched to perform an exam on the contralateral humerus, where investigator B identifies landmarks on the opposite side and investigator A times the exam.

After the conclusion of the exam on each arm the depth of each landmark under ultrasound will be noted, and the mid upper arm circumference will be measured.

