6.2 Secondary Analyses

We will estimate the median [Q1, Q3] of the mean time in seconds to identify all landmarks using ultrasound overall per patient overall and by BMI category.

Depth of each landmark will be summarized overall and by BMI category using appropriate summary statistics (e.g., mean \pm standard deviation and median [Q1, Q3]).

We will estimate the correlations between the following measures using Pearson correlation with 95% confidence intervals:

- Arm thickness with depth of anatomical structures
- BMI with depth of anatomical structures

Arm thickness, depth of anatomical structures, and BMI are only measured once per patient so standard methods are applicable (i.e., no repeated measures).

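### Second-exam times may be shortened because the second operator has watched the first exam; separately, operator pair, order and side are unallocated, so operator skill can be confounded with BMI cohort

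*Combined protocol and SAP*

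**What the plan says.** Section 4.1 General Design gives the procedure. "The study procedure will be performed on each patient by two out of three investigators", and the arms are divided between the two, "with one investigator examining each side". In the first exam investigator A scans, "while investigator B will time the exam starting from when the ultrasound probe is handled till all landmarks are identified". B does more than keep time: the "role is also to verify that landmarks are identified and document how many of the landmarks were seen". After that the two swap tasks for the other arm, so that "investigator B identifies landmarks on the opposite side and investigator A times the exam".

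The protocol does not say how the two investigators are chosen for a patient, who scans first, or which arm is scanned first. It mentions no randomisation, rotation or balancing of operators across BMI cohorts. Scores are kept per arm, but operator and exam order are not listed among the data to be collected.

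Section 6.2 Secondary Analyses summarises time as the "median [Q1, Q3] of the mean time in seconds to identify all landmarks using ultrasound", overall and by BMI category. Section 6.1 allows for correlation between the two exams of one patient through a bootstrap interval. Operator, order and side enter no analysis.

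**The concern.** There are two separate issues.

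**Preview.** The second operator cannot verify and count landmarks in the first exam without watching it. That operator then scans the opposite humerus of the same patient, having just seen where and how deep the structures lie. A shorter second exam is plausible. The planned per-patient mean mixes an exam without preview and an exam with it, and no analysis separates them. Time to identification is a secondary objective, and section 1.1 motivates the study by the need for fast access in resuscitation. There, no colleague would just have scanned the other arm.

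**Allocation.** With three operators, two per patient and 10 patients per cohort, one pair could by scheduling alone see most of one BMI cohort. Section 5.3 identifies participants by chart review, so BMI can be known before operators are assigned. The hypothesis in section 3 is that identification succeeds whatever the BMI, and results are reported by BMI category. A difference between operators could then appear as a difference between cohorts, or hide one. Unless operator and order are recorded, this could not be examined afterwards.

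**Working it through.** **Inputs from the documents.** 30 patients and 60 exams (Study Summary); 10 patients, so 20 exams, per BMI cohort (section 5.3); two of three operators per patient, one per arm (section 4.1); assumed success 80%, with 95% interval widths of 0.22 overall and 0.38 per cohort, ignoring intra-subject correlation (section 6.2 Sample Size Considerations). The documents give no figure for carry-over or for differences between operators, so the values used for those are assumptions.

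**The plan's own widths.** The exact (Clopper-Pearson) interval has lower limit Beta(0.025; x, n-x+1) and upper limit Beta(0.975; x+1, n-x).

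- x = 48, n = 60: width 0.2155, which rounds to 0.22.
- x = 16, n = 20: width 0.3793, which rounds to 0.38.

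Both stated figures are reproduced.

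**Preview.** Suppose both exams would take time T without preview, and preview shortens the second by a fraction d. The patient mean is (T + T(1-d))/2 = T(1 - d/2), an understatement of d/2. One exam in each patient is affected, 30 of 60 in all.

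| Assumed d | Understatement of the patient mean |
|---|---|
| 0 | 0 |
| 10% | 5% |
| 20% | 10% |
| 30% | 15% |

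Every patient has one first and one second exam. If d is the same in each cohort, all cohort times fall by the same proportion and preview creates no relative BMI difference. One arises only if d varies with BMI.

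**Allocation.** Let operator success rates be a ≥ b ≥ c. The best pair averages (a+b)/2 and the worst (b+c)/2. The largest gap between two cohorts due to operators alone is therefore (a-c)/2, half the spread. One operator can do between 0 and 10 of a cohort's 20 exams.

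- Assumed 90/80/70%: the three pair means are 85, 80 and 75%. The largest gap is 10 points, reached only if one cohort is seen wholly by the best pair and another wholly by the worst.
- Same rates, pairs falling at random: pair means deviate by +5, 0 or -5 points, with variance 50/3 = 16.67. The difference between two cohort means of 10 patients has variance 2 × 16.67/10 = 3.33, so the SD is about 1.8 points. In a simulation of 200,000 draws, a gap of 5 points or more occurred in about 0.8%.
- Same rates, pairs split 4/3/3 within each cohort: cohort means lie between (3×85 + 3×80 + 4×75)/10 = 79.5% and (4×85 + 3×80 + 3×75)/10 = 80.5%. The largest gap is 1 point.
- For time, with assumed operator means of 40, 60 and 80 s, pair means are 50, 60 and 70 s, a largest gap of 20 s.

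**Cost of using first exams only for success.** Exact widths at 80% are 0.31 for 24/30 overall (0.3085) and 0.53 for 8/10 per cohort (0.5309).

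**The case against.** The strongest reply is that these are possibilities and the documents do not show that either occurs. All operators have at least a year with the linear probe and "have participated in at least three (3) PHIO access workshops"; the second exam is on the other arm; and three pilot patients are left out of the analysis. The plan is descriptive, with no test between BMI groups. Under haphazard scheduling the operator artefact is small: an SD of 1.8 points, against a 95% half-width for a difference between two cohorts of 1.96 × √(2 × 0.16/20) = 0.248, or about 25 points. Nor is the remedy complete. Randomising order does not remove the preview, and 3 pairs × 2 orders × 2 sides make 12 cells for 10 patients per cohort.

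Much of this stands. A reader might infer that the times are biased downward, that machine settings carry over from one exam to the next, or that preview by itself distorts the BMI comparison. The documents support none of these. They contain no evidence on the presence or size of carry-over and do not mention machine settings, and carry-over of equal size would leave the BMI comparison intact.

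The reply does not remove the point. Training and pilot patients may narrow operator differences, but they neither stop the second operator from watching the first exam nor spread operators across cohorts. The random-scheduling figure describes a safeguard that the plan does not contain.

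**Conclusion.** The point holds as a design weakness; no bias has been demonstrated. The prescribed procedure may shorten second-exam times, and the planned mean would carry half of any such effect: 5-15% if the second exam is 10-30% faster, and 0 if there is no carry-over. That range rests wholly on the assumed reduction. It concerns the level of times, and the BMI comparison only if carry-over differs by BMI.

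Separately, operator skill is open to confounding with BMI cohort, by at most half the best-to-worst operator spread. The 10-point figure is a worst case on assumed rates of 90/80/70% with complete segregation of pairs by cohort. It should not be read as an expected gap, since nothing in the documents suggests that operators would cluster by BMI, though nothing prevents it. The stated interval widths of 0.22 and 0.38 are not in question.

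**What to change.** **Section 4.1.** Assign operator pair, first operator and first side from a list prepared in advance and randomised within each BMI cohort. Split the three pairs 4/3/3 in each cohort, so that each investigator does 6 or 7 of the 20 exams. Order and side can be balanced only approximately. Record operator, side and order for every exam.

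**Section 6.2 Secondary Analyses.** Report first-exam time, overall and by BMI cohort, beside the planned per-patient mean, as the estimate free of preview. Randomising the first operator matters here too, because otherwise first-exam time could reflect mainly one investigator.

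**Section 6.1.** Keep the primary success analysis on all 60 exams. Any split of success by exam order should be labelled descriptive, given exact widths of about 0.31 overall and 0.53 per cohort for first exams.

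**Cost.** A one-page list, three data fields and an extra table row. There is slightly less freedom in scheduling investigators, and the first-exam time rests on 30 exams (10 per cohort). Sample size and the stated widths do not change.
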